2.1. Study Design

This is a randomized, active controlled, parallel-group, open label study. Approximately 1500 subjects will be randomized 1:1 to apixaban or usual care (parenteral heparin and/or oral anticoagulation with Vitamin K antagonist (excluding other novel oral anticoagulants)). Following randomization, endpoints will be collected during the 30 days following the early cardioversion or during the 90 days post randomization if cardioversion is not performed within that time frame.

A schematic diagram below (Figure 1) shows the design of the study:

Figure 1 Study Design Schematic

Figure 1 Study Design Schematic

The Schedule of Activities table provides an overview of the protocol visits and procedures. Refer to [Study Procedures](#) and [Assessments](#) sections of the protocol for detailed information on each procedure and assessment required for compliance with the protocol.

The investigator may schedule visits (unplanned visits) in addition to those listed on the schedule of activities, in order to conduct evaluations or assessments required to protect the wellbeing of the subject.

Table 1 Schedule of Activities

Procedure	Visit 1 Enrollment Screening/Randomization ^a	Visit 2 Cardioversion	Visit 3 Follow-Up (30 days post cardioversion (Visit 2) or up to 90 days following Visit 1) ±7 days
Visit Windows			
Informed Consent	X		
Obtain Alternative Contact	X		
Inclusion/Exclusion	X		
Demographics	X		
Medical History	X		
CHA ₂ DS ₂ -VASc score ^b	X		
Local Laboratory Parameters	X	X	X
Randomization	X		
Cardioversion ^c		X	
Endpoint Assessments ^d		X	X
Dispense Study Drug	X	X	
Collect Study Drug		X	X
Study Drug Compliance Check		X	X
Adverse Event Assessment		X	X

^a Screening/Randomization could occur on the same day

^b CHA₂DS₂-VASc - Congestive heart failure, hypertension, age, diabetes, stroke, vascular disease, age, sex category risk score

^c Cardioversion details (timing, type, attempts, and rhythm status) and use of image guidance

^d Endpoints: stroke, systemic embolism, major bleeding, clinically relevant non-major bleeding, all cause death, and length of in-hospital stay

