6.4. Covariates

We have identified a number of baseline variables of interest:

- Age (continuous, in years),
- Hypertension (checkmark, Yes/No),
- Low Left Ventricular Function ($\leq 40\%$),
- Diabetes (Yes/No),
- Duration of Arrhythmia (in hours)

No imputation for missing data will be made on these covariates.

We will explore the effect of the above-mentioned covariates on all the clinical endpoints. Univariate analyses (one predictor at a time) and multivariate analyses (including all covariates from above and treatment effect) will be performed for the above mentioned covariates on each of the clinical endpoints using Cox proportional hazards models. Interaction tests between covariates and allocated treatment will be conducted.

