8.1.2 Analyses for Time-to-Event Data

Summaries will include tabular and graphical summaries of Kaplan-Meier estimates by treatment arm as well as hazard ratios of the treatment effect or other covariates, their 95% confidence intervals and p-values.

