8.1.3 Analyses for Binary Endpoints

For binary endpoints, 95% exact confidence intervals of each event rate will be reported by treatment group. The relative risk (risk ratios) will also be reported. In the SAS language we will use the RELRISK with FMSCORE method option in the EXACT statement of PROC FREQ in order to provide exact unconditional confidence limits for the relative risk.

Other binary data comparisons will be made using Fisher’s exact test.

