8.2.4. Analyses of Clinical Endpoints

- *Stroke.*
- *Systemic embolism.*
- *Major Bleeding.*
- *Clinically Relevant Non-Major Bleeding.*
- *All cause death.*

The following time periods will be defined for reporting clinical endpoints:

- Pre-cardioversion
- Post-cardioversion
- ALL: entire duration (include 30 days follow-up after cardioversion).

The characterization of stroke, systemic embolism and death will be done based on the adjudicated endpoints during the study (according to an intention-to-treat paradigm). Analysis of these endpoints will be based on the full analysis set.

The characterization of bleeding will be done with a focus on adjudicated major bleeding and clinically relevant non-major bleeding during the treatment period (according to a safety paradigm). Analysis of these endpoints will be based on the safety analysis set.

The clinical endpoint summaries will include descriptive statistics of individual event rates and their exact 95% confidence intervals; however exact risk ratios and corresponding p-values comparing the treatment arms will also be presented without any formal testing.

Sensitivity analysis: If the TEE/TOE or CT procedures will identify subjects with thrombus (thrombus-positive), sensitivity analyses of all clinical endpoints will be run on a dataset obtained by removing those subjects from the Full Analysis Set. The dataset from which thrombus-positive (as per investigator’s assessment) subjects were excluded will be labeled as Full Prevention-Evaluable; its complementary set of Thrombus Positive-ITT will be analyzed for the endpoints of Stroke, Systemic Embolism, and Death. Sensitivity analyses of bleeding events will also be run on a dataset (labeled as Safety Prevention-Evaluable Analysis Set) obtained by removing subjects with thrombus (as per investigator’s assessment) from Safety analysis set; its complementary set of Thrombus Positive-Safety will be analyzed for the bleeding endpoints.

The Modified Full Analysis set will be analyzed for the endpoints of Stroke, Systemic Embolism, and Death.

Subgroup analyses: Clinical endpoints and safety (AEs, SAEs) will be reported for each subgroup of interest. Subgroups of interest are (please note that bleeding endpoints are based on the safety analysis set while the others are based on the full analysis set):

- “Early Cardioversion” (defined as cardioversion that occurs within 7 days from randomization),
- Image Guidance (TEE/TOE or CT),

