- age (< 65 years old, ≥ 65 years old)
- gender.
- For the clinical endpoints (stroke/embolism/death), also analyze by (first) cardioversion status: ‘Interventional cardioversion’, no cardioversion, or ‘Spontaneous cardioversion’
- For clinical endpoints, breakdown summaries by Apixaban initial dose levels (loading dose vs. no loading dose) will be produced.

We will display graphically the Kaplan-Meier product-limit estimators of the time to

- Composite of first adjudicated stroke or systemic embolism,
- First Major bleeding event,
- Composite of first major bleeding and clinically relevant non-major bleeding
- All cause death.

8.2.5. Other analyses:

The full analysis set will be used to summarize data on cardioversion details, length of in-hospital stay and usage of image guidance.

- Cardioversion details will be summarized by number of attempts (a separate table will be presented for each number of attempts).
 - The summary for first attempt will be based on the full analysis set. Timing of cardioversion will be the time from randomization to the first attempt only, with time to first attempt censored at the last day of follow-up if an attempt has not been made.
 - The hazards ratio (and p-value) will be calculated for time from randomization to the first attempt at cardioversion, comparing image guided to non-image guided subjects.
 - The second attempt will be summarized based on the subset of the full analysis set that already had the first cardioversion, etc.

- For each attempt we will summarize the number and proportion of subjects with cardioversion attempts and the number and proportion with each rhythm status.
 - Demog/baseline tables will be subset for 1) subjects with no cardioversion attempt, 2) subjects with one cardioversion attempt, and 3) subjects with 2 or more cardioversion attempts
- Length of in-hospital stay is defined as the number of hours from hospital admission to hospital discharge following cardioversion. The date and time of all hospital admissions and discharges following cardioversion will be captured within the CRF at Visit 2 and 3. Frequency of hospital stay, mean and median duration will be summarized by treatment arm.
 - Early cardioversion is defined as cardioversion that occurred within the first 7 days after randomization. Frequency and proportions will be reported by treatment arm.

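### SAP 8.2.4 appears to compare arms before cardioversion by subject counts with p-values, although the length of that period is set after randomisation and no time-based analysis is tied to it

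*SAP*

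**What the plan says.** SAP 8.2.4 introduces the periods with "The following time periods will be defined for reporting clinical endpoints" and lists Pre-cardioversion, Post-cardioversion and "ALL: entire duration (include 30 days follow-up after cardioversion". Later in the same section it plans event rates with exact 95% intervals and adds that "exact risk ratios and corresponding p-values comparing the treatment arms will also be presented without any formal testing". SAP 8.1.3 gives the method: PROC FREQ, with "exact unconditional confidence limits for the relative risk". That works on a table of subjects, so time at risk does not enter.

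Follow-up varies by subject. SAP 2.1 states that "endpoints will be collected during the 30 days following the early cardioversion or during the 90 days post randomization if cardioversion is not performed".

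Time-based analyses are planned elsewhere:
- SAP 8.1.2: Kaplan-Meier estimates by arm and "hazard ratios of the treatment effect or other covariates, their 95% confidence intervals and p-values".
- SAP 6.4: covariate and treatment effects "on each of the clinical endpoints using Cox proportional hazards models".
- SAP 8.2.4: Kaplan-Meier displays for four outcomes.
- SAP 8.2.5: a censored time to first attempt ("Timing of cardioversion will be the time from randomization to the first attempt only"). The hazard ratio named there compares image-guided with non-image-guided subjects.

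None of these is tied to the three reporting periods. The SAP also does not say whether the time and events of never-cardioverted subjects count as Pre-cardioversion, or which date divides the periods after spontaneous conversion.

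**The concern.** A ratio of subject counts compares like with like only if both arms are observed for similar lengths of time. Post-cardioversion meets this for subjects who are cardioverted. Pre-cardioversion does not have to, because it ends at an event that happens after randomisation, or runs to day 90 if that event never happens.

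A difference by arm is plausible. The trial is open label. Protocol 5.2.3.2 offers an apixaban loading dose where cardioversion comes early (not in Japan), while Protocol 5.2.3.1 has vitamin K antagonist dosing follow the INR. Usual care may also use heparin, so the direction cannot be predicted.

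If the wait differs, more events before cardioversion in one arm may show only that its subjects waited longer. A p-value against a ratio of 1 then has no clear meaning. Pre-cardioversion is also the one unequal period without a time-based counterpart to set beside the count.

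**Working it through.** **Figures in the plan.** There is no forecast of timing by arm to reproduce. Protocol 9.1 predicts 1 and 3 strokes or systemic emboli, (1+3)/1500 = 0.27% (stated as about 0.3%), and 2 and 5 major bleeds, (2+5)/1500 = 0.47% (stated as about 0.45%). Both agree with the text, apart from rounding.

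**Inputs from the documents.** 750 per arm (about 1500, 1:1); follow-up to 30 days after cardioversion, or 90 days without it; mean times to cardioversion of 3.0 days (TEE-guided) and 30.6 days (conventional) in the trial cited in Protocol 1.2, which compares imaging strategies and not these arms.

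**Assumptions.** The same constant hazard in both arms, fixed times to cardioversion, and the shares shown below, which appear nowhere in the documents.

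**Formula.** For rare events at equal hazard, the expected count ratio is the ratio of mean days at risk per randomised subject. Mean Pre days = sum of share × days to cardioversion, with 90 days for those never cardioverted.

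| Scenario | First arm, Pre days | Second arm, Pre days | Ratio | Arms swapped |
|---|---|---|---|---|
| (i) image-guided/conventional/never 80/10/10% vs 70/20/10% | 0.8×3.0 + 0.1×30.6 + 0.1×90 = 14.46 | 0.7×3.0 + 0.2×30.6 + 0.1×90 = 17.22 | 0.84 | 1.19 |
| (ii) day 3 vs day 7, 10% never in both | 0.9×3 + 0.1×90 = 11.70 | 0.9×7 + 0.1×90 = 15.30 | 0.76 | 1.31 |
| (iii) day 3 in both, 10% vs 15% never | 0.9×3 + 0.1×90 = 11.70 | 0.85×3 + 0.15×90 = 16.05 | 0.73 | 1.37 |

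Events per person-day give a Pre ratio of 1.00 in all three.

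**Effect of the unstated rule.** If never-cardioverted subjects are left out of Pre-cardioversion, (i) becomes 5.46/8.22 = 0.66 and (ii) becomes 3/7 = 0.43.

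**Size in events, scenario (ii), a gap of 15.30 − 11.70 = 3.60 days.**
- At 6.01% per year (major or clinically relevant non-major bleeding on warfarin, Protocol 1.2): 750 × 0.0601/365.25 × 11.70 = 1.44 versus 1.89 events, a shift of 0.44.
- At 2.9% over eight weeks (hemorrhagic events in the cited TEE trial, Protocol 1.2): 750 × 0.029/56 × 3.60 = 1.4.
- At 5.5% over eight weeks: 750 × 0.055/56 × 3.60 = 2.7.

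**Does the same argument apply to ALL?** Add 30 days for each cardioverted subject. Three risk patterns were tried, with equal hazards between arms. The hazard ratio is the Cox score-equation solution in the rare-event limit.

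| Risk pattern | Crude ALL ratio (i)/(ii)/(iii) | Hazard ratio (i)/(ii)/(iii) |
|---|---|---|
| Constant | 0.938 / 0.915 / 0.931 | 1.00 / 1.00 / 1.00 |
| 5-fold for 30 days after cardioversion | 0.982 / 0.976 / 1.022 | 1.045 / 1.086 / 1.042 |
| All risk after cardioversion | 1.000 / 1.000 / 1.059 | 1.064 / 1.121 / 1.059 |

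Under a constant hazard only the crude ratio moves. When risk follows the procedure, the hazard ratio is further from 1 in five of the six cases and tied in the sixth. Wherever the Pre and Post person-time rate ratios are defined, they equal 1.00.

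**The case against.** **The study is descriptive.** SAP 4.1 and 4.2 set no hypotheses or decision rules, and the ratios are described as involving no formal testing. This stands and limits the harm. P-values are still to be printed, and a descriptive table still needs comparable denominators.

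**Ratios per period are an inference.** No sentence requires them. The paragraphs just before the ratio sentence speak of stroke, embolism and death over the study and of bleeding over the treatment period, so whole-study ratios are a possible reading. This stands as a caveat. The periods are, however, defined for reporting these same endpoints.

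**Time at risk is already handled.** For ALL it largely is, through the hazard ratios, Cox models and Kaplan-Meier curves. A reader might infer that the crude ALL ratio is faulty and that the hazard ratio should replace it. That does not follow. The crude ALL risk validly describes the assigned strategy, because events during a longer wait belong to it. Protocol 1.2 describes thromboembolic risk associated with cardioversion itself, and when risk clusters there the hazard ratio does no better than the crude ratio in any case tried.

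**More observation means more events.** A reader might infer that the arm watched longer always shows the higher crude risk. In scenario (iii) with risk clustered after the procedure, the arm watched longer (41.55 versus 38.70 days) has the lower crude ALL risk.

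**The imbalances are assumed.** This stands. The figures show sensitivity and are not a forecast.

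**Conclusion.** The point holds for Pre-cardioversion and is minor. On the natural reading, the plan compares arms by counts with p-values over a period whose length is set after randomisation, with no time-based analysis attached. Under equal constant hazards the ratio falls to 0.73–0.84, or rises to 1.19–1.37 with the arms swapped, in the assumed scenarios. It stays at 1 if timing and completion are alike in both arms. In the day 3 versus day 7 example the shift is about 0.4 events at 6.01% per year and about 1.4 to 2.7 events at the cited hemorrhagic rates, whose endpoint definition may differ from this trial's.

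The documents do not support a claim that the trial's overall comparison is biased in a known direction, or that the plan ignores time at risk altogether.

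**What to change.** In SAP 8.2.4:
1. For Pre- and Post-cardioversion, report person-time and events per person-time by arm beside the counts: full analysis set for stroke, embolism and death; safety set and treatment period for bleeding.
2. Give the crude Pre-cardioversion risk ratio without a p-value.
3. State that never-cardioverted subjects contribute time and events to Pre-cardioversion up to day 90, and which date divides the periods for spontaneous conversion. For those subjects Protocol 5.2.3 counts 30 days of treatment from Visit 2; the SAP should say whether it uses the same date.
4. Show the time to first attempt from SAP 8.2.5, by arm, next to the endpoint table.
5. Leave ALL as planned, with the crude ratio, the hazard ratio and the Kaplan-Meier curves read together and none replacing another.

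The cost is SAP wording and a little programming. The planned time-to-event analyses already need the randomisation, cardioversion, event and last follow-up dates. Two limits should be stated with the results: the Pre rate assumes a steady hazard before cardioversion, and the Post rate conditions on having been cardioverted.

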#### **9.4. Independent Adjudication**

Independent Adjudicator(s) will review and adjudicate all clinical endpoints and positive TEE/TOE or CT without awareness of treatment allocation, ie, in a blinded manner. The responsibilities and procedures followed are described in the Adjudication Charter.

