5.4. Other Analysis Sets

Prevention-evaluable analyses datasets will be created in order to exclude subjects identified at visit 2 through imaging as already having a thrombus; if multiple evaluations took place over time for a subject, only the first one will be used.

The Full Prevention-Evaluable Analysis Set is obtained by excluding thrombus-positive subjects from the Full Analysis Set. The Safety Prevention-Evaluable Analysis Set is obtained by removing subjects with thrombus from the Safety Analysis Set. The sets of Thrombus Positive-Full Analysis Set and Thrombus Positive-Safety are the complements of the Full Prevention-Evaluable and Safety Prevention-evaluable subjects.

The Modified Full Analysis Set is the subset of the Full Analysis Set of subjects that received at least one study drug dose.

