Routine hemoglobin and serum creatinine will be recorded within the CRF from Visit 1 to Visit 3. The data will be presented in listings without imputations and displaying even multiple findings per visit. The lab data will not be summarized.

Compliance for apixaban will be reported and summarized overall. The compliance formula is: $\# \text{tablets taken} / (\# \text{of days} * 2 + L)$ where $L=1$ if loading dose was given and 0 otherwise.

INR will be summarized for the usual care arm. Rosendaal's linear interpolation methodology will be used to determine the proportion of time in specified INR range and time to therapeutic range (i.e. time from randomization to the first INR greater than or equal to 2).

Time to withdrawal will be analyzed and displayed as a KM figure.

For the adjudicated TEEs, we will report the concordance/discordance between investigator's assessment and the adjudicator's assessment, without regard to treatment arm. Details of the adjudicated TEEs will be included in a listing, as well as details of the investigator's initial TEE assessment.

Demogs/baseline characteristics will be summarized for the following groups: 10 mg load vs no load, 5 mg load vs. no load, 10 mg load vs 5 mg load

Demogs/baseline characteristics will be compared for spontaneous vs. interventional cardioversion within the Apixaban arm.

Demogs/baseline characteristics will be compared for spontaneous vs. interventional cardioversion within the usual care arm.

Demogs/baseline characteristics will be compared for spontaneous vs. interventional cardioversion in the two treatment arms combined.

Demogs/baseline characteristics will be compared for electrical vs. pharmacological vs. both cardioversion within the Apixaban arm.

Demogs/baseline characteristics will be compared for electrical vs. pharmacological vs. both cardioversion within the usual care arm.

Demogs/baseline characteristics will be compared for electrical vs. pharmacological vs. both cardioversion in the two treatment arms combined.

Demogs/baseline characteristics will be compared for subjects with thrombus vs. subjects without thrombus.

The following analyses/comparisons will be performed for each of the clinical endpoints; the Full Analysis Set will be used for stroke, systemic embolism, and for death, while the safety dataset will be used for the bleeding endpoints;

for the following Apixaban groups: 10 mg load vs no load, 5 mg load vs. no load, 10 mg load vs 5 mg load

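### The thrombus-based sensitivity sets rest on the unblinded investigator's image reading, although a blinded reading of every positive image is available

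*SAP*

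**What the plan says.** The study is randomized 1:1 and open label (Protocol 3; SAP 2.1).

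**Definition of the sets.** SAP 5.4 creates prevention-evaluable sets that leave out subjects "identified at visit 2 through imaging as already having a thrombus". It adds that "if multiple evaluations took place over time for a subject, only the first one will be used". Section 5.4 names no reader. SAP 8.2.4 does: the full set is "The dataset from which thrombus-positive (as per investigator’s assessment) subjects were excluded", and the safety set is "obtained by removing subjects with thrombus (as per investigator’s assessment) from Safety analysis set". The thrombus-positive complements are then analysed for stroke, systemic embolism and death (full set) and for bleeding (safety set).

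**The blinded reading.** Protocol 9.4 says that independent adjudicators "will review and adjudicate all clinical endpoints and positive TEE/TOE or CT without awareness of treatment allocation". Protocol 6.5 confirms that it is the positive images that are sent.

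**What the blinded reading is used for.** In SAP 8.2.5 "we will report the concordance/discordance between" the two readings. That report covers adjudicated TEEs only and is pooled over the arms; a listing accompanies it. The same section compares subjects with and without thrombus on baseline characteristics and on every clinical endpoint, and does not say whose reading decides.

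**The concern.** A sensitivity analysis should test the main result without adding a bias of its own. Here, membership depends on a judgement made after randomization by someone who can know the treatment. If knowledge of the arm influences how readily an equivocal image is called positive, the two arms lose different kinds or numbers of subjects.

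The plan protects the endpoints against this by blinded adjudication. It does not extend that protection to the decision on who is counted, although a blinded reading exists for every image that can trigger an exclusion. The planned concordance report would not expose a difference between arms, because it is pooled, and it leaves out CT although positive CTs are adjudicated too.

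At stake is how far the prevention-evaluable and thrombus-positive results can be trusted, not the trial's main results.

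**Working it through.** **1. The plan's own figure.** Protocol 9.1 predicts 1 stroke or systemic embolism event on apixaban and 3 on usual care among 1500 subjects. (1 + 3) / 1500 = 0.27%, which rounds to the stated 0.3%. The concern does not depend on this figure; it only shows how few events there are.

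**2. The passages side by side.**
- Who decides exclusion: the investigator (SAP 8.2.4), in an open-label study.
- When: at Visit 2, after randomization at Visit 1, on the first evaluation (SAP 5.4). Protocol 5.2.3.2 places apixaban dosing before image-guided cardioversion, so treatment has normally begun.
- Which images also have a blinded reading: every investigator-positive one and no investigator-negative one (Protocol 6.5 and 9.4).
- Which set the blinded reading defines: none. It feeds a pooled TEE concordance report and a listing (SAP 8.2.5).

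**3. Sensitivity to a single exclusion.** Risk ratio = (a / 750) / (u / 750), with a and u the apixaban and usual-care events and about 750 subjects per arm. Excluding a few subjects barely changes the denominators.
- 1 vs 3, as predicted: 0.33 (Fisher p = 0.62)
- 1 vs 2, one usual-care event excluded: 0.50
- 1 vs 1, two usual-care events excluded: 1.00
- 0 vs 3, the apixaban event excluded: 0

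**4. How large could an arm difference in exclusions be?** The documents give no imaging share, thrombus prevalence or reader error rates, so these are assumptions: share imaged f = 40 to 80%, prevalence p = 3 to 10%, equal reader sensitivity of 95% in both arms, and false-positive rates (apixaban vs usual care) of 2% vs 2%, 1% vs 3%, or 0% vs 4%. The direction is arbitrary. With equal sensitivity, true positives cancel and

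difference in exclusions = 750 × f × (1 − p) × (difference in false-positive rates).

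- Equal rates: 0
- Smallest unequal case: 750 × 0.40 × 0.90 × 0.02 = 5.4 subjects
- Largest: 750 × 0.80 × 0.97 × 0.04 = 23.3 subjects

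If those extra subjects carried the predicted average usual-care risk of 3/750, the expected number of events removed would be 5.4 × 3/750 = 0.02 to 23.3 × 3/750 = 0.09. On these assumptions, losing even one event this way is unlikely. Subjects called positive may carry a different risk; the documents do not say.

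**5. What the blinded reading repairs.** If adjudication rejects the false positives, the difference in step 4 falls to 0. Differential misses remain, because negative images are never re-read. Assuming sensitivities of 90% vs 98%, the leftover imbalance is 750 × f × p × 0.08, from 750 × 0.40 × 0.03 × 0.08 = 0.7 to 750 × 0.80 × 0.10 × 0.08 = 4.8 subjects.

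**The case against.** The strongest reply is that the investigator's reading is a legitimate definition. Under Protocol 6.5 the management expected after an image suggesting thrombus follows from the local reading, and Protocol 1.2 describes a pragmatic trial. A subject called positive locally and not confirmed later may still have been managed as having a thrombus. This stands, and is why the investigator-based sets should stay. It also means that unconfirmed subjects should not be described as wrongly excluded.

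The reach is small. The study is descriptive, with no hypothesis test or decision rule, and stroke, systemic embolism and death are analysed on all randomized subjects with blinded adjudication. This stands and sets the severity.

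Part of the requested output is implicit already. The thrombus-positive sets are analysed, and event rates are reported by treatment group (SAP 8.1.3), so their denominators show the investigator-based exclusions per arm. True. But those counts cannot separate unconfirmed calls from real differences in thrombus, and the pooled concordance does not help.

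On timing, using only the first image and the expectation in Protocol 1.2 that most image-guided cardioversions come within hours to days both limit the problem. Changing the reader does not address timing at all.

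A reader might also infer from the concordance report that the SAP expects misreadings. It does not say so; such a report is ordinary quality reporting.

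**Conclusion.** The point holds as a low-severity improvement. Both prevention-evaluable sets and their complements are defined by an unblinded, post-randomization reading, while the blinded reading of every positive image defines no set. Differential false-positive calls could therefore make exclusions differ by arm in these sensitivity analyses.

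Three stronger readings are tempting, and the documents do not support them:
- That exclusions do differ by arm. Nothing in the documents shows this or suggests a direction.
- That the trial's main results are affected. They use the full and safety sets, which do not depend on thrombus status.
- That the adjudicated reading would give an unbiased set. It cannot recover missed thrombi, it does not turn thrombus status into a baseline variable, and subjects who were not imaged stay in the prevention-evaluable set whichever reader is used.

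No size can be derived from the documents. A total of unconfirmed calls would not supply one either, since equal over-calling in both arms produces no imbalance. The move in the risk ratio from 0.33 to 0.50 shows only how fragile a comparison of 1 versus 3 predicted events is; it does not estimate bias. The range of 5 to 23 subjects rests entirely on the assumed rates.

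**What to change.** In SAP 5.4 and 8.2.4, keep the investigator-based sets and add a second version of each prevention-evaluable and thrombus-positive set in which only adjudicator-confirmed thrombus counts as positive. Run the 8.2.4 endpoints on both versions.

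Report by arm: the number excluded under each definition; the time from randomization to the first image; and investigator-adjudicator concordance for TEE and CT.

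State the limits beside these tables: negative images are not adjudicated, so differential misses are not corrected, and thrombus status remains a post-randomization variable. Name the reader in 5.4 and in the with-versus-without-thrombus comparisons of 8.2.5.

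The cost is a few extra tables and some SAP text. No new image readings are needed, because all positive images are already adjudicated.
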